
Figure 6. Hazard curves for incident of Heart Failure among 5,958 MESA participants stratified according to the presence or absence of hypertension (prevalence=45%) or the presence or absence of "high" reflection magnitude (top 45% of the population). Hazard curves are adjusted for other significant predictors of HF in this population. From: [name] JA et al, *J Am Coll Cardiol*: 60:2170-2177.

Targeting Central Hemodynamics in CKD Pilot Study
Protocol Version 003, February 15, 2016

highly desirable goal from the clinical and public health perspective. In order to design a definitive proof of concept trial, we must first establish the optimal dose of ISMN to reduce wave reflections independently of blood pressure and to assess the variability in study endpoints in response to ISMN in this particular population, such that adequate power calculations can be made.

C. RESEARCH DESIGN AND METHODS

C.1. Overview of study design

This is a pilot study in which we will study 20 subjects with CKD. We will perform a run-in phase in which the dose of sustained-release ISMN (SR-ISMN) will be increased from 30 to 120 mg over weeks. We will administer 30 mg for 1 week, followed by 60 mg for 1 week, followed by 120 for 1 week. At the end of each week, we will perform detailed assessments of blood pressure and central hemodynamics. We will assign half of the participants to receive vitamin C (500 mg three times daily) to assess whether this intervention reduces nitrate tolerance.

After the initial 3-week run in phase, we will randomly assign subjects to receive either 60 or 120 mg of SR-ISMN for additional 21 weeks (for a total of 24 weeks of therapy). Half of the subjects will continue to receive vitamin C (500 mg three times daily by mouth) throughout this 21-week period. We will assess the effect of our interventions on late systolic load, LV mass, LV fibrosis, diastolic relaxation and quality of life.

After subjects are identified and demonstrate an interest in the research study, inclusion and exclusion criteria will be assessed and if eligible, the patients will undergo written informed consent and enrolled in the study.

C.2 Study Sites

The two sites for this trial will be the Hospital of the University of Pennsylvania and the Penn Presbyterian Medical Center. Both sites share a single Institutional Review Board.

C.3. Study Population

[figure not shown]

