Blood Draw: Blood samples will be obtained in order to measure serum creatinine and hematocrit prior to each cardiac MRI. In addition, samples will be centrifuged and frozen at -80 degrees C to perform proteomics analysis using the Somascan platform, which measures ~1300 plasma proteins. We will also collect a spot urine sample (~50 cc) in every study visit.

C.5. Run-in phase and ISMN initiation

Subjects will first undergo a run-in phase to assess within subject responses to ISMN at doses of 30 mg, 60 mg and 120 mg daily (with or without ascorbic acid), which will be better powered than between-arm comparisons. Half the subjects will be randomly assigned to receive ascorbic acid (500 mg by mouth three times daily).

- After baseline assessments, ISMN will be initiated at a dose of 30 mg daily (with or without ascorbic acid).
- **1-week visit:** Subjects will undergo a brief visit for peripheral, central BP and arterial stiffness measurements (arterial tonometry and VaSera device measurements) after ~1 week (5-9 days). ISMN will be increased to 60 mg daily. Blood (20 cc) and urine (~50 cc) will also be sampled and frozen.
- **2-week visit:** Subjects will undergo a brief visit for peripheral, central BP and arterial stiffness measurements (arterial tonometry and VaSera device

measurements) after ~1 week (5-9 days). ISMN will be increased to 120 mg daily. Blood (20 cc) and urine (~50 cc) will also be sampled and frozen.

- **3-week visit:** Subjects will undergo a brief visit for peripheral, central BP and arterial stiffness measurements (arterial tonometry and VaSera device measurements) after ~1 week (5-9 days). Subjects will also undergo a Doppler echocardiogram during this visit. A 24 hour ambulatory BP monitoring Blood (20 cc) and urine (~50 cc) will also be sampled and frozen.

In all cases, up-titration will occur only if:

- (1) Resting supine systolic blood pressure is ≥ 95 mmHg;
- (2) There is no evidence of orthostatic hypotension (decrease ≥ 20 mmHg in systolic or ≥ 10 mmHg in diastolic blood pressure within 3 minutes of standing);⁶³
- (3) The subject is not experiencing dizziness, vertigo, or other symptoms that, in the opinion of the investigator, may be due to the vasoactive effect of the drugs.

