If the drug is not tolerated, subjects will be discontinued from the study. After completion of the run-in phase, subjects will be assigned to different doses of SR-ISMN (60 and 120 mg of SR ISMN daily) for additional 21 weeks (10 subjects per dose). Patients will continue taking ascorbic acid according to their initial allocation to receive or to not receive vitamin C. The design will therefore be a 2x2 factorial, such that 5 subjects will be allocated to ISMN SR 60- mg without vitamin C, 5 subjects will be allocated to ISMN SR 60- mg with vitamin C, 5 subjects will be allocated to ISMN SR 120- mg without vitamin C, and 5 subjects will be allocated to ISMN SR 120- mg with vitamin C. The intervention will be open label, but endpoint assessments will be blinded.

C.6. 12-week visit

The 12-week visit will take place in which we will perform:

- An office BP measurement
- Arterial tonometry and VaSera measurements
- A 2d Echocardiogram
- 24 hour ambulatory BP monitoring and pulse wave analysis monitoring
- A blood draw and urine sample

C.7. Final (24-week) assessments:

After the end of the 24 weeks therapy, arterial tonometry, VaSera measurements, Doppler echocardiography, cardiac MRI, 24-hour BP / pulse wave analysis monitoring, and blood draws will be repeated after the end of 21 weeks of fixed dose ISMN SR therapy (with or without vitamin C), to assess for changes in response to the study intervention. Procedures will be identical to those performed during the baseline assessment.

C8. Adverse Event Reporting

Targeting Central Hemodynamics in CKD Pilot Study
Protocol Version 003, February 15, 2016

All adverse events will be reported following institutional guidelines. The research team will keep a log of all adverse events that occur in the trial, and any reportable events will be handled accordingly. The study team in charge of the conduct of the trial is up to date on all trainings pertaining to safety guidelines and adverse event reporting. All Serious Adverse Events will be reported to the site review boards, the Data Safety Monitoring Board, as well as the NIH in a timely fashion.

C.7. Data Management

The data for this trial will be collected by the research staff during each visit that the subject attends. Specific forms have been developed for the questions in this trial and will be filled out via pen and paper. Later, this data will be entered into a database developed in RedCap.

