All data collected in this trial will be housed inside of a locked cabinet in the office space of the research staff, located at Ravdin 2 (Cardiovascular Institute).

C.8. Early termination

Subjects who withdraw due to intolerable adverse events or other safety concerns, or simply because they no longer wish to participate in the trial, will undergo a termination visit in which we will document: (1) vital signs; (2) compliance with the medications, including pill count; (3) Adverse effects. (4) specific reason for withdrawal.

D. Statistical Considerations

All study outcomes are continuous measures, thus, least-square regression models will be used to estimate effect sizes associated with each intervention. For the run-in phase, we will use mixed models to assess within subject changes to 30- 60 and 120 mg, and also to assess the effect of ascorbic acid on this response.

Analysis of the changes at 24 weeks between the study arms will also be assessed with mixed models to assess the following: (1) whether there are any significant within group changes in the outcome measures (from baseline to the final visit) in response to nitrate therapy at 30, 60 or 120 mg; (2) To test whether the outcome improvement in response to combination therapy is different between the 2 doses; (3) Whether vitamin C appears to have any effect on the responses. We recognize that this is a pilot study and therefore we will pay particular attention to the variability in the response and will interpret trends conservatively, particularly when confidence intervals are wide enough to be inconclusive. We note that, even though there is limited power for the inferential analyses, the data from this study will be critical to perform power calculations and propose a definitive trial, as per the aims of our R56 award. MRI endpoints will involve only 2 measures (baseline Targeting Central Hemodynamics in CKD Pilot Study

Protocol Version 003, February 15, 2016

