and 24-weeks). However, echocardiographic and tonometry measures will involve three measurements per subject during the long-term phase (baseline, 12-week and 24-week visit). These will be modeled for intervention effects using general linear modeling on the intent-to-treat population.^{64, 65} Subject-specific intercepts and slopes will be included as random effects; variability in the actual timing of assessments will be explicitly included in the mixed model by analyzing time as a random effect. Individual growth parameters will be modeled as a function of group, time, and the interaction of group and time. Differences in reflection magnitude over time will be examined via inferential testing of the “group by time” interaction term. Restricted maximum likelihood estimation will be used, and an appropriate covariance matrix will be specified. Linear and quadratic mixed models will be examined. The Akaike information criterion⁶⁶ will be used to evaluate overall model fit and to select the best-fitting longitudinal change pattern. For dropouts, the mechanism for missingness will be evaluated. If the number of subjects lost to follow-up is small and the missing observations can be documented as being missing at random (MAR) or missing completely at random (MCAR), analyses will be performed using the complete observed data. More complex approaches will be considered, such as random pattern-mixture models if necessary.^{67, 68} Sensitivity analyses for these models will be performed.⁶⁹ We will use parsimonious linear models to assess whether the reduction in reflection magnitude predicts the improvement in individual outcomes (LV mass, LV collagen volume fraction, LV diastolic relaxation velocity). Bootstrapping procedures will be used to obtain estimates of the effects and to test their significance via confidence intervals.⁷⁰ Analyses will be 1-tailed since we hypothesize specific directions to the relationships or changes in measured parameters between baseline and 24 weeks post-initiation of long-term therapy.

F. PROTECTION OF HUMAN SUBJECTS

F.1. RISKS TO THE SUBJECTS

Human Subjects Involvement and Characteristics

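### The randomised dose and vitamin C comparisons are planned without baseline adjustment, which costs some precision unless baseline and follow-up are very highly correlated

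*Combined protocol and SAP*

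**What the plan says.** Two factors are randomised. Vitamin C is allocated at the start of the run-in (C.5). Dose is allocated after it: "we will randomly assign subjects to receive either 60 or 120 mg of SR-ISMN for additional 21 weeks" (C.1). C.5 adds that "The design will therefore be a 2x2 factorial", with "10 subjects per dose" and five per cell, so each factor compares 10 with 10.

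For the comparison of arms, Section D says "Analysis of the changes at 24 weeks between the study arms will also be assessed with mixed models". The questions listed there include whether the two doses differ and whether vitamin C has an effect. MRI endpoints have two measurements, baseline and week 24. Echo and tonometry have three in the long-term phase: baseline, week 12 and week 24. The longitudinal model follows the sentence on echo and tonometry: "Subject-specific intercepts and slopes will be included as random effects", and "Individual growth parameters will be modeled as a function of group, time, and the interaction of group and time". The test is named for one endpoint only: "Differences in reflection magnitude over time will be examined via inferential testing of the" group-by-time term.

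Section D nowhere enters the baseline value as a covariate, and nowhere constrains arm means to be equal at baseline. Its opening mention of least-squares regression lists no covariates. It gives no alpha, effect size, SD or correlation. It does say that the tests are one-tailed and that power for inference is limited.

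**The concern.** Week 0 precedes both randomisations, so the arms have the same expected baseline mean. A model with a free group term estimates that difference from 20 people instead of using the fact that it is zero by design. The contrast then ignores how far a subject's baseline predicts the follow-up value, and part of any chance baseline gap enters the estimate, because the arm that starts high tends to fall more.

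The study has few subjects, and its dose comparison is meant to inform the later trial. Precision available from data already collected should be used unless there is a reason not to.

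**Working it through.** **Inputs.** From the documents: N = 20, 10 vs 10 on each factor, week 0 before both randomisations, one-tailed tests. Assumed, because the documents are silent: rho from 0.3 to 0.95, equal SD at both visits, no dropout, one-sided alpha 0.05 and an effect of 0.8 baseline SD. The plan states no power figure, so there is none to reproduce.

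**1. What the planned contrast estimates.** With two visits and a free group term, group by time is the difference in mean raw change. With equally spaced visits at weeks 0, 12 and 24, a linear slope gives week 12 zero weight, so with complete data under compound symmetry the slope contrast is again the week 0 to 24 change.

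**2. Variance, in units of the baseline variance.**
- Change: 2(1 − rho).
- Baseline-adjusted: 1 − rho².
- Large-sample ratio, adjusted to change: (1 + rho)/2.

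Estimating the baseline slope adds a cost. With intercept, dose and vitamin C in the model, 17 residual degrees of freedom remain, and the ratio is multiplied by 1 + 1/(17 − 2) = 1.067. At rho 0.5 this gives 0.75 × 1.067 = 0.80. The break-even is (1 + rho)/2 = 15/16, so rho is about 0.88.

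**3. Simulation of the 20-subject 2x2 design.** Variance and half-width are ratios of adjusted to change. Half-widths are for two-sided 95% intervals. Power is one-sided 5% for 0.8 SD.

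| rho | variance | half-width | power, change | power, adjusted |
|---|---|---|---|---|
| 0.3 | 0.69 | 0.83 | 43% | 54% |
| 0.5 | 0.80 | 0.90 | 53% | 61% |
| 0.7 | 0.89 | 0.96 | 72% | 76% |
| 0.8 | 0.96 | 0.98 | 86% | 87% |
| 0.9 | 1.00 | 1.01 | 99% | 98% |
| 0.95 | 1.04 | 1.02 | 100% | 100% |

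A second simulation gave 52% and 60% for power at rho 0.5.

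**4. Three-visit model.** Generalised least squares with linear time and known covariance gives variance ratios, common to free baseline, of 0.60, 0.73, 0.84 and 0.95 at rho 0.3, 0.5, 0.7 and 0.9. With an added random-slope variance of 0.2 they are 0.65, 0.77, 0.88 and 0.97. These omit the small-sample cost in step 2.

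**5. Chance imbalance.** The SE of the baseline difference is √(2/10) = 0.447 SD. The probability of a gap above 0.5 SD is 2(1 − Φ(0.5/0.447)) = 0.264. Given a gap, the change contrast moves by (1 − rho) times it, in the opposite direction. For a gap of 0.5 SD the shift is 0.25 SD at rho 0.5, 0.15 at 0.7 and 0.05 at 0.9. Simulated slopes of the estimate on the gap were −0.71, −0.51, −0.31 and −0.10 at rho 0.3, 0.5, 0.7 and 0.9, and about zero after adjustment.

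**6. Week 3, dose contrast only.** Echo and tonometry are also measured at week 3 (schedule in Appendix II), before the dose randomisation. If all visits are equally correlated (an assumption), adjusting for weeks 0 and 3 gives half-width ratios of 0.88 at rho 0.5 and 0.91 at rho 0.7, against 0.90 and 0.96 with week 0 alone.

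**The case against.** Several objections stand in whole or in part.

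- **Validity.** A reader might infer that chance imbalance biases the planned comparison. It does not. Across randomisations the change contrast is unbiased, and its interval already allows for variation in baseline. The shift in step 5 is conditional on the imbalance drawn.
- **Scope.** A reader might infer that every endpoint, LV mass included, is tested by group by time. Section D states that model for echo and tonometry, and the test for reflection magnitude only. For MRI, the point rests on the reference to changes and on the absence of any baseline term; the wording does not exclude one. The plan also leaves undefined whether group means four cells or two factors.
- **Week 3.** A reader might infer that the week-3 values go unused. They can enter the run-in mixed models, and Section D does not define baseline for the long-term phase. Week 0 is the natural reading given C.4, but it is a reading.
- **Size.** The gain depends on an unknown rho. A highly repeatable endpoint, as LV mass may be, could gain nothing. Fewer than 20 completers would raise the cost of the extra term, and C.5 discontinues subjects who do not tolerate the drug.
- **Importance.** The primary aims are the variability of change, for which raw change is the right target, and Section D already promises cautious interpretation. A narrowing of 10% would not make 10-vs-10 comparisons decisive.

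None of this gives a reason to prefer the unadjusted contrast for endpoints with moderate rho. It limits the point to the efficiency of secondary comparisons.

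**Conclusion.** The point holds as one of efficiency. For echo and tonometry, the stated model yields an unadjusted change contrast. For MRI, baseline adjustment is not specified. With 20 completers and equal SDs, adjustment narrows the interval by about 17%, 10%, 4% and 2% at assumed rho of 0.3, 0.5, 0.7 and 0.8, and widens it by 1–2% at 0.9 or more. One-sided 5% power for 0.8 SD at rho 0.5 rises from about 53% to about 60%; alpha and effect size are assumptions. Adjustment also removes the conditional shift from baseline imbalance. The balance favours adjustment, because the possible loss is small and the possible gain is larger. The documents do not support calling the planned test invalid, nor extending the point to the primary variability estimates.

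**What to change.** In Section D, for the between-arm dose and vitamin C contrasts only:

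- **MRI endpoints:** regress the week-24 value on its baseline value, dose and vitamin C.
- **Echo and tonometry:** either constrain arm means to be equal at week 0 (time coded zero there, no group main effect, group-by-time terms kept), or use the week-0 value as a covariate and the later visits as outcomes. Write dose and vitamin C as separate factors in place of the undefined group.
- **Optional, dose contrast only:** also adjust for the week-3 echo or tonometry value, after stating that baseline in the long-term model means week 0. This needs a separate dose model, because week 3 falls after the vitamin C randomisation and must not be adjusted for in that contrast.
- Keep the primary variability estimates on raw change.

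The cost is one degree of freedom for baseline and a second where week 3 is used. With baseline adjustment alone, intervals may be up to about 2% wider for endpoints with rho of 0.9 or more. No new data or visits are needed.

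### Section D names only REML but picks a linear or quadratic time shape by AIC: read that way the comparison is invalid, and the week-24 dose contrast should be fixed under either shape

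*Combined protocol and SAP*

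**What the plan says.** Section D (Statistical Considerations) sets the MRI endpoints apart, because they have two measures per subject. For the others, "echocardiographic and tonometry measures will involve three measurements per subject during the long-term phase (baseline, 12-week and 24-week visit"). These three-visit measures get growth models with subject-specific random intercepts and slopes, and "Individual growth parameters will be modeled as a function of group, time, and the interaction of group and time". On visit timing, "variability in the actual timing of assessments will be explicitly included in the mixed model by analyzing time as a random effect".

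On fitting, "Restricted maximum likelihood estimation will be used, and an appropriate covariance matrix will be specified. Linear and quadratic mixed models will be examined". The next sentence says that the AIC "will be used to evaluate overall model fit and to select the best-fitting longitudinal change pattern". ML is not named in the section. No model time unit, time origin or outcome scale is given, and a group by time-squared term is not among those listed.

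The inferential test is written for reflection magnitude: "Differences in reflection magnitude over time will be examined via inferential testing of the" group-by-time interaction. Earlier in section D the target is a change: "Analysis of the changes at 24 weeks between the study arms will also be assessed with mixed models", covering change from baseline to the last visit within groups and the difference between the two doses. The plan does not link that target to a term in the selected model.

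**The concern.** There are two separate gaps.

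- **Selection.** Linear and quadratic mean shapes have different fixed effects. The REML likelihood contains a term that depends on the fixed-effect design, so REML values from the two models are not on a common scale. If AIC is computed from the REML fits, the choice of shape can turn on the units in which outcome and time are recorded.
- **Tested term.** In the linear model, group-by-time is the dose difference in the baseline-to-week-24 change. In a quadratic model it may be something else, depending on which terms are added and where time zero lies. The plan does not say which quantity is then tested.

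At stake are the test of reflection magnitude, which is the mechanistic target, and the models for the other echocardiographic and tonometry measures. These include early diastolic mitral annular velocity, part of co-primary aim 1c.

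**Working it through.** The plan gives no power, SD, alpha or AIC figure on this point, so there is none to reproduce.

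**Inputs from the documents.** Visits at 0, 12 and 24 weeks; random intercept and slope; REML; AIC selection between linear and quadratic (section D). 20 subjects, 10 per dose (section C.5). One-tailed tests (section D).

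**Step 1: REML-AIC moves with the units.** With N observations and p fixed effects,

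-2 log REML = (N - p) ln 2π + ln det V + ln det(X'V⁻¹X) + r'V⁻¹r,

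and one form of REML also subtracts ln det(X'X). The plan does not say which form applies. Let k be the number of extra quadratic columns: 1 for a common time-squared, 2 if group by time-squared is added.

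- *Outcome multiplied by s.* ln det V gains 2N ln s and ln det(X'V⁻¹X) loses 2p ln s. The AIC difference (quadratic minus linear) therefore shifts by -2k ln s. For s = 10 and k = 2: -4 × 2.3026 = -9.21. ln det(X'X) does not involve the outcome, so the shift is the same in both REML forms.
- *Time multiplied by c.* Each quadratic column is multiplied by c², which adds 4 ln c to ln det(X'V⁻¹X). The shift is 4k ln c. Subtracting ln det(X'X) cancels it, so this affects only the form without that term.

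| Time rescaling (form without ln det(X'X)) | k = 2 | k = 1 |
|---|---|---|
| weeks to days, c = 7 | 8 ln 7 = +15.6 | 4 ln 7 = +7.8 |
| weeks to months, c = 1/4 (24 weeks taken as 6 months) | 8 ln(1/4) = -11.1 | 4 ln(1/4) = -5.5 |

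ML has no ln det(X'V⁻¹X) term and the same N in both models, so its AIC difference shifts by 0 in either case.

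**Step 2: no general selection rate exists under REML-AIC.** As an illustration, 100 simulated trials per setting were run with time in weeks, k = 2, the form without ln det(X'X), assumed variances, and both doses changing by 1 SD by week 12 and holding it. With the outcome multiplied by 0.1, 1, 10 and 100, the quadratic was chosen in 0%, 0-6%, 8-57% and 67-97% of trials (range over assumed correlations and AIC penalties). Any single rate holds only for its assumed outcome scale.

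**Step 3: what group-by-time measures.** The weights at weeks 0, 12 and 24, scaled to a 24-week change, are:

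| Model | Weights |
|---|---|
| linear | (-1, 0, +1) |
| quadratic, common time-squared only | (-1, 0, +1) |
| quadratic with group by time-squared, time zero at baseline | (-3, +4, -1) |
| quadratic with group by time-squared, time centred at week 12 | (-1, 0, +1) |

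Take a true week-24 dose difference of 1. The (-3, +4, -1) term returns 4(0.5) - 1 = 1 if the difference grows linearly, 4(1) - 1 = 3 if it is complete by week 12, and 4(0) - 1 = -1 if it arises only after week 12.

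**Step 4: illustrative power.** Assumptions: a dose difference of 1 SD of the 24-week change, one-sided 5%, equal independent visit errors, t with 18 df. The SE ratio is √(26/2) = 3.6.

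- Week-24 contrast: noncentrality 1/√0.2 = 2.24, power 69%.
- (-3, +4, -1) term: power 15%, 56% and 1% for the three courses in step 3.

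Those figures are conditional on the quadratic being chosen and that term being tested. Averaged over ML-AIC selection, for a difference growing linearly to 1 SD (500 simulated trials, assumed within-subject correlation about 0.5 or 0.8), testing the linear term gives 58% and 83%. Fixing the week-24 contrast gives 63% and 92%. The loss is 62.8 - 58.2 = 4.6 and 91.8 - 82.8 = 9.0 points.

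**Step 5: the estimate itself.** With complete, on-time visits, both shapes estimate the week-24 dose difference in change with weights (-1, 0, +1), so it is identical. They diverge only with missing or off-schedule visits. Suppose a dose difference of 1 SD at week 12 has gone by week 24 and the linear shape is kept. With 2 week-24 values missing per dose, the bias is 0.11-0.13 SD; with 3 missing on one dose, it is 0.19-0.22 SD. The SE is 0.33-0.50. All of these inputs are assumed.

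**The case against.** The strongest reply has three parts. First, section D never says that AIC will be taken from the REML fits; a careful analyst would use ML for the comparison and keep REML for the final estimates. Second, group by time-squared is not among the listed terms, and with a common time-squared term the tested quantity does not change. Section D also names change at 24 weeks as its target. Third, the consequences are small: the primary aims concern variability, and section D acknowledges limited power and promises conservative interpretation.

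All of this limits the weight of the point. It does not remove it. REML is the only method named, and the plan neither rules out the interaction with time-squared nor ties the test to the 24-week change. Complete visits cannot be presumed either, since the plan itself expects losses: "For dropouts, the mechanism for missingness will be evaluated".

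Some stronger readings are tempting and are not supported:

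- *That an invalid comparison will certainly be run.* The text leaves the likelihood behind the AIC unstated.
- *That REML-AIC would mostly miss real curvature, or would never switch wrongly to a quadratic.* Either depends on the outcome scale and time unit, and the plan gives neither.
- *That the month labels in Appendix II show time would be modelled in months.* They stand in the list worded for patients. The schedule of events in the same appendix uses Week 12 and Week 24, as do sections C and D.
- *That the tested quantity is undefined whenever the quadratic is chosen.* This requires group by time-squared and a time origin that changes the term's meaning, such as baseline.

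**Conclusion.** The point holds in conditional form and merits correction. If AIC comes from the REML fits, as the text reads, the choice between linear and quadratic is invalid. That result is algebraic and needs no assumed effect or SD: the AIC difference shifts by -2k ln s with the outcome unit in either REML form, and by 4k ln c with the time unit in the form without ln det(X'X). If group by time-squared is included with time zero at baseline, group-by-time no longer measures the change that section D sets as its target.

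The practical effect is modest. The week-24 estimate is unchanged with complete, on-time visits. The power loss after ML selection is about 5 to 9 points, and the bias under assumed missingness is smaller than its SE. Both rest on assumed variances, effect courses and a one-sided 5% level. The MRI endpoints are unaffected. A reader might infer that the pilot as a whole is undermined; the documents do not support that.

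**What to change.** In section D:

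1. Compare the linear and quadratic shapes by AIC from ML fits, then refit the chosen model by REML.
2. State whether the quadratic model includes group by time-squared.
3. Fix the dose comparison in advance as the model-based difference in change from baseline to week 24, whichever shape is chosen, and report the week-12 difference beside it.

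The third item is needed even with ML: in simulations under assumed variances, ML-AIC still chose the quadratic in about 18-20% of trials with a truly linear course.

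The cost is a few sentences and one extra ML fit per shape and outcome, with no new data or visits. The one downside is that the week-24 contrast does not detect a difference present only at week 12, hence the separate week-12 report. An acceptable alternative is visit as a category with baseline adjustment. It needs no shape selection but gives up the planned modelling of actual visit timing and subject-specific slopes.
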